8.5. Evaluating of Adverse Events

An Investigator who is a qualified physician will evaluate all adverse events with respect to the elements outlined in [Table 6](#). The Investigator's assessment of causality is required for each adverse event. Refer to [Table 6](#) for instructions in evaluating adverse events.

Table 6. Evaluating Adverse Events

| | | |
|--|--|--|
| Maximum | Mild | awareness of sign or symptom, but easily tolerated (for pediatric trials, awareness of symptom, but easily tolerated) |
| Intensity | Moderate | discomfort enough to cause interference with usual activity (for pediatric trials, definitely acting like something is wrong) |
| | Severe | incapacitating with inability to work or do usual activity (for pediatric trials, extremely distressed or unable to do usual activities) |
| Seriousness | A serious adverse event (AE) is any adverse event occurring at any dose or during any use of Sponsor's product that: | |
| | †Results in death; or | |
| | † Is life threatening; or places the subject, in the view of the Investigator, at immediate risk of death from the event as it occurred [Note: This does not include an adverse event that, had it occurred in a more severe form, might have caused death.]; or | |
| | † Results in a persistent or significant disability/incapacity (substantial disruption of one's ability to conduct normal life functions); or | |
| | † Results in or prolongs an existing inpatient hospitalization (hospitalization is defined as an inpatient admission, regardless of length of stay, even if the hospitalization is a precautionary measure for continued observation. (Note: Hospitalization for an elective procedure to treat a pre-existing condition that has not worsened is not a serious adverse event. A pre-existing condition is a clinical condition that is diagnosed prior to the use of a Merck product and is documented in the patient's medical history); or | |
| | † Is a congenital anomaly/birth defect (in offspring of subject taking the product regardless of time to diagnosis); or | |
| | Is a cancer; or | |
| | Is associated with an overdose (whether accidental or intentional). Any adverse event associated with an overdose is considered a serious adverse event. An overdose that is not associated with an adverse event is considered a non-serious event of clinical interest and must be reported within 24 hours. | |
| Other important medical events that may not result in death, not be life threatening, or not require hospitalization may be considered a serious adverse event when, based upon appropriate medical judgment, the event may jeopardize the subject and may require medical or surgical intervention to prevent one of the outcomes listed previously (designated above by a †). | | |

090177e1848ce2dd\Approved\Approved On: 23-Sep-2013 15:48

090177e1848ce2dd\Approved\Approved On: 23-Sep-2013 15:48

| | | |
|-----------------------------------|--|--|
| Duration | Record the start and stop dates of the adverse event. If less than 1 day, indicate the appropriate length of time and units | |
| Action taken | Did the adverse event cause the Sponsor's product to be discontinued? | |
| Relationship to Sponsor's Product | 
Did the Sponsor's product cause the adverse event? The determination of the likelihood that the Sponsor's product caused the adverse event will be provided by an Investigator who is a qualified physician. The Investigator's signed/dated initials on the source document or worksheet that supports the causality noted on the AE form, ensures that a medically qualified assessment of causality was done. This initialed document must be retained for the required regulatory time frame. The criteria below are intended as reference guidelines to assist the Investigator in assessing the likelihood of a relationship between the test drug and the adverse event based upon the available information.
 
The following components are to be used to assess the relationship between the Sponsor's product and the AE; the greater the correlation with the components and their respective elements (in number and/or intensity), the more likely the Sponsor's product caused the adverse event:
 | |
| | Exposure | Is there evidence that the subject was actually exposed to the Sponsor's product such as: reliable history, acceptable compliance assessment (pill count, diary, etc.), expected pharmacologic effect, or measurement of drug/metabolite in bodily specimen? |
| | Time Course | 
Did the AE follow in a reasonable temporal sequence from administration of the Sponsor's product?
 
Is the time of onset of the AE compatible with a drug-induced effect (applies to trials with investigational medicinal product)?
 |
| | Likely Cause | Is the AE not reasonably explained by another etiology such as underlying disease, other drug(s)/vaccine(s), or other host or environmental factors |
| Relationship to Sponsor's Product | The following components are to be used to assess the relationship between the Sponsor's product and the AE: (continued) | |
| (continued) | Dechallenge | 
Was the Sponsor's product discontinued or dose/exposure/frequency reduced?
 
If yes, did the AE resolve or improve? If yes, this is a positive dechallenge. If no, this is a negative dechallenge.
 
(Note: This criterion is not applicable if: (1) the AE resulted in death or permanent disability; (2) the AE resolved/improved despite continuation of the Sponsor's product; (3) the trial is a single-dose drug trial); or (4) Sponsor's product(s) is/are only used one time.)
 |

090177e1848ce2dd\Approved\Approved On: 23-Sep-2013 15:48

| | |
|---|--|
| Rechallenge | 
Was the subject re-exposed to the Sponsor's product in this trial?
 
If yes, did the AE recur or worsen?
 
If yes, this is a positive rechallenge. If no, this is a negative rechallenge.
 
(Note: This criterion is not applicable if: (1) the initial AE resulted in death or permanent disability, or (2) the trial is a single-dose drug trial); or (3) Sponsor's product(s) is/are used only one time.)
 
NOTE: IF A RECHALLENGE IS PLANNED FOR AN ADVERSE EVENT WHICH WAS SERIOUS AND WHICH MAY HAVE BEEN CAUSED BY THE SPONSOR'S PRODUCT, OR IF RE-EXPOSURE TO THE SPONSOR'S PRODUCT POSES ADDITIONAL POTENTIAL SIGNIFICANT RISK TO THE SUBJECT THEN THE RECHALLENGE MUST BE APPROVED IN ADVANCE BY THE U.S. CLINICAL MONITOR AND THE INSTITUTIONAL REVIEW BOARD/INDEPENDENT ETHICS COMMITTEE.
 |
| Consistency with Trial Treatment Profile | 
Is the clinical/pathological presentation of the AE consistent with previous knowledge regarding the Sponsor's product or drug class pharmacology or toxicology?
 |
| 
The assessment of relationship will be reported on the case report forms /worksheets by an Investigator who is a qualified physician according to his/her best clinical judgment, including consideration of the above elements.
 | |
| Record one of the following: | 
Use the following scale of criteria as guidance (not all criteria must be present to be indicative of a Sponsor's product relationship).
 |
| Yes, there is a reasonable possibility of Sponsor's product relationship. | 
There is evidence of exposure to the Sponsor's product. The temporal sequence of the AE onset relative to the administration of the Sponsor's product is reasonable. The AE is more likely explained by the Sponsor's product than by another cause.
 |
| No, there is not a reasonable possibility of Sponsor's product relationship | 
Subject did not receive the Sponsor's product OR temporal sequence of the AE onset relative to administration of the Sponsor's product is not reasonable OR there is another obvious cause of the AE. (Also entered for a subject with overdose without an associated AE.)
 |

8.6. Events of Clinical Interest

Selected non-serious and serious adverse events are also known as Events of Clinical Interest (ECI) and must be recorded as such on the Adverse Event case report forms/worksheets and reported within 24 hours to Pfizer or designee either by electronic media or paper. Appropriate contact information can be found in the Investigator Trial File Binder (or equivalent).

Events of clinical interest for this trial include:

1. An overdose of Sponsor's product, as defined in [Section 8.2](#), that is not associated with clinical symptoms or abnormal laboratory results.
2. An elevated AST or ALT lab value that is greater than or equal to 3X the upper limit of normal and an elevated total bilirubin lab value that is greater than or equal to 2X the upper limit of normal and, at the same time, an alkaline phosphatase lab value that is less than 2X the upper limit of normal, as determined by way of protocol-specified laboratory testing or unscheduled laboratory testing.*

*Note: These criteria are based upon available regulatory guidance documents. The purpose of the criteria is to specify a threshold of abnormal hepatic tests that may require an additional evaluation for an underlying etiology. The trial site guidance for assessment and follow up of these criteria can be found in the Investigator Trial File Binder (or equivalent).

8.7. Management of Subjects with Elevated Liver Enzymes (ALT or AST $\geq 3X$ ULN)

Section I: Identification and Management of Subjects with ALT or AST Results $\geq 3X$ ULN

Increases in ALT or AST $\geq 3X$ the upper limit of normal (ULN) are defined as clinically significant for this study. The central laboratory report will alert the Investigator if a subject meets this threshold. When a randomized subject who is receiving investigational study drug has an ALT or AST elevation beyond the clinical significant margin above, the Investigator should monitor the subject according to the instructions below and discontinue the subject from investigational study drug if a pre-specified criterion is met.

The Investigator should select the appropriate set of instructions (either A, B, or C below) for managing a subject with elevated liver enzymes based upon the following factors: (1) the magnitude of a subject's ALT or AST elevation, (2) the presence or absence of symptoms, (3) whether there is a corresponding increase in total bilirubin (TBL) $\geq 2X$ ULN.

Investigator Instructions for Management of Subjects with ALT or AST $\geq 3X$ ULN

| |
|---|
| A) Subject has: 
• ALT or AST $\geq 3X$ ULN with TBL $\geq 2X$ ULN and alkaline phosphatase (ALP) $< 2X$ ULN |
| 
1. The subject should interrupt investigational study drug.2. Refer to the “Event of Clinical Interest (ECI) Guidance for Potential DILI (Drug-Induced Liver Injury) in Clinical Trials” (located in the Investigator Trial File Binder or equivalent) and perform procedures accordingly.3. If an etiology for the elevated ALT or AST and TBL levels is established and the abnormalities resolve, investigational study drug may be restarted with approval by the Sponsor. Otherwise, the subject should discontinue treatment with investigational study drug. 
Note: Laboratory assessments prescribed in the Event of Clinical Interest (ECI) Guidance for Potential DILI (Drug-Induced Liver Injury) in Clinical Trials may be sent locally in emergent cases and to support subject compliance with the necessary evaluations. Subjects unwilling to undergo the prescribed testing should be discontinued from treatment with investigational study drug.
 |

| |
|--|
| B) Subject has: 
• ALT or AST $\geq 8X$ ULN OR• ALT or AST $\geq 3X$ ULN and signs or symptoms of a drug reaction consistent with liver injury (eg, fever, eosinophilia, right upper quadrant pain, dark urine, fatigue, etc.) |
| 
1. The subject should interrupt investigational study drug.2. Perform repeat ALT and AST within 3 days of receipt of the laboratory report.3. Initiate evaluation for potential causes. See Section II below.4. Repeat ALT and AST tests at appropriate intervals, initially approximately 2-times per week, until resolution or return to baseline.5. If an etiology for the elevated liver enzymes is established (eg, active hepatitis with specific etiology demonstrated, cholecystitis, biliary obstruction), investigational study drug may be restarted with approval by the Sponsor. Otherwise, the subject should discontinue treatment with investigational study drug. 
Note: Local laboratory assessments can be used to support compliance with the repeat testing procedure described above if required. Subjects unwilling to undergo repeat ALT and AST testing at the frequency recommended above should be discontinued from treatment with investigational study drug.
 |

090177e1848ce2ddApproved\Approved On: 23-Sep-2013 15:48

C) Subject has:

- **ALT or AST $\geq 3X$ and $< 8X$ ULN**

1. For subjects with:

ALT or AST $\geq 3X$ and $< 5X$ ULN:

- Perform repeat ALT and AST within 3-5 days of receipt of the laboratory report.

OR

ALT or AST $\geq 5X$ ULN and $< 8X$ ULN:

- Perform repeat ALT and AST within 3 days of receipt of the laboratory report. Subjects unable to undergo repeat measurements within 3 days must interrupt study drug.

2. Initiate evaluation for potential causes. See Section II below.

3. Actions based upon *initial* repeat testing:

If **ALT or AST $\geq 3X$ ULN with TBL $\geq 2X$ ULN**, then interrupt investigational study drug and monitor as described in Section A Instructions above and also per “*Event of Clinical Interest (ECI) Guidance for Potential DILI (Drug-Induced Liver Injury) in Clinical Trials*” (located in the Investigator Trial File Binder or equivalent) and perform procedures accordingly.

If **ALT or AST $\geq 8X$ ULN or ALT or AST $\geq 3X$ ULN with symptoms** present (eg, fever, eosinophilia, right upper quadrant pain, dark urine, fatigue, etc.), then interrupt investigational study drug and monitor as described in Section B Instructions above.

If **ALT or AST $\geq 3X$ ULN and $< 8X$ ULN** (without above criteria met), continue to measure ALT and AST 1- to 2-times per week (2-times per week if ALT or AST $\geq 5X$ ULN or if an increase $> 20\%$ occurred since the first elevated value[s]).

If **ALT and AST $> ULN$ and $< 3X$ ULN**, perform repeat determination in 5-7 days, and then at appropriate intervals (eg, every other week) until the subject’s ALT and AST levels are within normal limits or are similar to baseline.

4. Actions based upon *follow-up* repeat testing:

If **ALT or AST $\geq 5X$ ULN** after 2 weeks, *discontinue investigational study drug*.

If **ALT or AST remain elevated** ($\geq 3X$ and $< 5X$ ULN) but stable, the frequency of retesting can decrease (eg, every other week) with approval from the Sponsor.

If **ALT and AST $> ULN$ and $< 3X$ ULN**, perform repeat determination in 5-7 days, and then at appropriate intervals (eg, every other week) until the subject’s ALT and AST levels are within normal limits or are similar to baseline.

Note: Local laboratory assessments can be used to support compliance with the repeat testing procedures described above if required. Subjects unwilling to undergo repeat ALT and AST testing at the frequency defined above should be discontinued from treatment with investigational study drug.

In summary, subjects should be discontinued from investigational study drug for any of the following reasons:

- ALT or AST $\geq 3X$ ULN with TBL $\geq 2X$ ULN and ALP $< 2X$ ULN and without an established etiology.
- ALT or AST $\geq 8X$ ULN or $\geq 3X$ ULN with symptoms consistent with liver injury and without an established etiology.
- ALT or AST $\geq 5X$ ULN for 2 weeks.

Section II: Guidance for Assessment of Potential Etiology

Questions to Assess Etiology

Investigate potential causes for the subject's elevated liver enzymes using the questions below. Answers to the questions should be recorded in the subject's source documents and appropriate eCRFs.

1. Has the subject recently:
 - Had a change in his/her pattern of alcohol use? Investigate historic pattern of alcohol use as well.
 - Administered an illegal drug(s) (including intravenous drugs)?
 - Been exposed to a chemical agent or other environmental toxin?
 - Consumed any unusual foods (eg, mushrooms), seasonal foods, or initiated treatment with new herbal/nutritional supplements?
 - Initiated a new diet regimen, started a rigorous exercise program, or experienced any form of severe physical exertion?
 - Traveled to another country or region?
2. Does the subject have a relevant concomitant illness (eg, cholelithiasis, hepatitis, etc.) or has the subject had potential exposure to viral hepatitis (transfusion, tattoo, new sexual partner)?

3. Does the subject have a relevant medical history (eg, autoimmune disorder, cancer, Gilbert's syndrome, obesity, Wilson's disease, Non-alcoholic steatohepatitis (NASH), alcoholic or infectious hepatitis, biliary tract disease, hypoxic/ischemic hepatopathy, etc.)?
4. Has the subject recently been treated with a concomitant medication(s) with demonstrated or suspected effects on the liver (eg, acetaminophen; amiodarone; aspirin; chlorpromazine; dantrolene; erythromycin; halothane; isoniazid; methyl dopa; nitrofurantoin; oxyphenisatin; perhexiline maleate; phenytoin; propylthiouracil; rifampin; sulfonamides; tetracyclines) or initiated treatment with another new medication(s)?

Additional Laboratory/Imaging Evaluations

In subjects for whom an etiology for the abnormal liver enzymes is unknown or whose elevated liver enzymes persist for more than 1-week:

1. Consider performing serologic tests including: (a) Hepatitis A (IgM); (b) Hepatitis B (surface antigen and core IgM); (c) Hepatitis C (antibody); (d) Hepatitis E (IgG and IgM). Obtain consent prior to testing, if required locally. Additional evaluations may be performed at the discretion of the Investigator.
2. Consider an ultrasound of the subject's right upper quadrant and additional scans (endoscopic retrograde cholangiopancreatography [ERCP] or magnetic resonance cholangiopancreatography [MRCP]) if needed.

Note: Subjects may also be referred to a gastroenterologist or hepatologist for an additional work-up if considered necessary by the Investigator.

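### Section 8.7 liver rule: Box C interrupts drug on a bilirubin result that its repeat tests do not order, and the ALP condition is not the same across the boxes and the summary list

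*Combined protocol and SAP*

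**What the plan says.** Section 8.7 gives three sets of investigator instructions, called Boxes A, B and C here, and then a summary list of reasons to discontinue. Section 6.7.2 item 3 relies on this section for stopping drug because of abnormal liver tests.

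- **Selection factors** (before the boxes): size of the ALT/AST elevation, symptoms, and whether TBL is at least 2X ULN. ALP is not among them.
- **Box A**: ALT/AST at least 3X with TBL at least 2X and "alkaline phosphatase (ALP) $< 2X$ ULN". Drug is interrupted at once. Step 3 allows a restart only if a cause is found and the abnormalities resolve; otherwise drug is discontinued.
- **Box B**: ALT/AST at least 8X, or at least 3X with symptoms. Drug is interrupted. ALP plays no part.
- **Box C**: ALT/AST from 3X to below 8X. Step 1 says, for 3X to below 5X, "Perform repeat ALT and AST within 3-5 days of receipt of the laboratory report". For 5X to below 8X the same two tests are due within 3 days, and "Subjects unable to undergo repeat measurements within 3 days must interrupt study drug". Step 3 covers the initial repeat: if ALT/AST is at least 3X with TBL at least 2X, "then interrupt investigational study drug and monitor as described in Section A Instructions above". If no trigger is met and enzymes are still in range, the site is to "continue to measure ALT and AST 1- to 2-times per week". Step 4 covers follow-up repeats. It stops drug at 5X or more after 2 weeks, allows less frequent testing for stable values from 3X to below 5X, and does not mention TBL.
- **Summary list**: bullet 1 needs ALT/AST at least 3X, TBL at least 2X, and "ALP $< 2X$ ULN and without an established etiology". Bullet 3 is "ALT or AST $\geq 5X$ ULN for 2 weeks".
- **Section 8.6**: the hepatic event of clinical interest also requires ALP below 2X ULN.

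**The concern.** There are two linked problems in a binding safety rule.

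First, one of the interruption triggers uses a test that the rule does not order. The subject most exposed enters Box C with TBL below 2X and then develops a raised TBL while ALT/AST stay up. That is the change step 3 is meant to catch, and repeats of ALT and AST alone cannot show it. Nor can they identify the Section 8.6 event, which needs the TBL and ALP values at the same time as the enzyme value.

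Second, ALP is a condition in some places and absent in others. For an asymptomatic subject with ALT/AST from 3X to below 8X, TBL at least 2X and ALP at least 2X, the first-result box, the repeat step and the summary list give different answers. Sites may act differently on the same result.

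What is at stake is how long a subject with possible liver injury stays on drug, and whether sites apply the rule alike.

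**Working it through.** The plan gives no figure on this point, so the check is a trace of the rule.

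**Tests ordered against tests used in Box C**

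| Step | Tests ordered | Tests the decision needs |
|---|---|---|
| 1, first repeat | ALT, AST | n/a |
| 3, action on first repeat | n/a | ALT, AST and TBL |
| 3, continued monitoring | ALT, AST | n/a |
| 4, action on follow-up repeats | n/a | ALT, AST (no TBL branch) |

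Section II of 8.7 does not name TBL or ALP; it lists serology and imaging to consider and leaves further evaluations to the investigator.

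Read literally, the next TBL comes with the next scheduled chemistry panel. The Schedule of Activities has chemistry at Weeks 6, 12, 18, 26, 39, 52, 65, 78, 91 and 104. The gaps are 6, 6, 8, 13, 13, 13, 13, 13 and 13 weeks, and 6 weeks from Day 1 to Week 6. The nominal interval is therefore 6 to 13 weeks. A rescue or early termination visit would bring a panel sooner. Meanwhile Box C draws blood 1 to 2 times per week, so 2 weeks x 1 to 2 = 2 to 4 draws, all ordered for ALT and AST only. At 5X or more, step 4 and bullet 3 end treatment at 2 weeks whatever the TBL. From 3X to below 5X no such limit applies, and stable subjects can move to testing every other week.

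**ALP condition**

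Take ALT/AST in 3 bands (3X to <5X, 5X to <8X, at least 8X), symptoms no/yes, TBL below or at least 2X, and ALP below or at least 2X. That gives 3 x 2 x 2 x 2 = 24 combinations, 12 of them with ALP at least 2X. Assign each to the boxes, to step 3 (assuming identical values on repeat and TBL measured), and to the summary bullets. All 24 fall in at least one box. Two conflict, the second and third rows below.

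| Profile, no symptoms | First result | Repeat, TBL measured | Summary list |
|---|---|---|---|
| 3X to <8X, TBL at least 2X, ALP <2X | Box A: interrupt | already interrupted | bullet 1 |
| 3X to <5X, TBL at least 2X, ALP at least 2X | Box C: continue and repeat | step 3: interrupt, go to Section A | not listed |
| 5X to <8X, TBL at least 2X, ALP at least 2X | Box C: continue (interrupt if no repeat within 3 days) | step 3: interrupt, go to Section A | bullet 3 only, at 2 weeks |
| 3X to <8X, TBL <2X then at least 2X | Box C: continue | step 3: interrupt | bullet 1 only if ALP <2X; bullet 3 if at least 5X for 2 weeks |

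If TBL is measured on the first repeat, the two conflicting profiles are interrupted within 3 to 5 days of the report (3X to <5X) or within 3 days (5X to <8X). The last row is the first problem again: the interruption depends on a test not ordered.

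**Box A step 3 against summary bullet 1**

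Box A discontinues unless a cause is found and the abnormalities resolve. Bullet 1 lists only the absence of a cause. A subject with a known cause and unresolved tests is discontinued by the box but not listed in the summary. Box B step 5 and bullet 2 both turn on cause alone, so they do match.

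**The case against.** Several replies carry weight.

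- *TBL will be available anyway.* TBL and ALP sit with ALT and AST in the Table 5 chemistry panel, so a scheduled first result carries them, and Section 8.6 contemplates unscheduled testing. Step 3 does not say that its TBL must come from the repeat sample. This stands for a subject whose first TBL was already at least 2X: a site could combine that value with the repeat ALT/AST. A reader might infer that such a subject cannot be classified at all, but the text does not force that reading. The reply does not help a subject whose TBL rises later. Nor is a full panel assured on the repeat, because Box C lets sites use local laboratories.
- *Every subject has an action.* True. A reader might infer that the rule leaves ALP at least 2X without any action. It does not: Boxes B and C have no ALP condition, and step 3 interrupts whatever the ALP. The fault is conflicting directions. Likewise, Section I is not silent on ALP, since the boxes and summary sit under that heading; only its selection factors omit it.
- *The sequence may be deliberate.* Waiting for confirmation of a mixed picture and then interrupting is a coherent policy. The referral to Section A can supply the stopping rule, and the reasons in Section 6.7.2 are not exhaustive. So the summary should not be read as permitting drug to continue. It remains a list that does not match the boxes, and the text does not state the policy.
- *The site binder may settle it.* The ECI guidance is not among the documents and may add tests. Box C points to it only after the TBL trigger is met, so it does not send the site there to order the repeat TBL.
- *Investigators can stop drug.* Section 6.7.2 item 8 allows this, and Box B covers symptoms and values of 8X or more. Both limit the harm without correcting the rule.

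**Conclusion.** The point holds as two wording defects in a safety rule. (1) Box C has an interruption trigger that its own ordered tests cannot detect when TBL was below 2X at first and rises later, and step 4 drops the trigger altogether. (2) The ALP condition is applied unevenly, which gives 2 of 24 combinations a sequence of continue, interrupt, and then absence from summary bullet 1. For the 5X to below 8X band, bullet 3 closes the summary gap at 2 weeks.

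Few subjects are likely to be affected, and the documents give no rate. A reader might try to derive one from Section 1.4, which reports 479 exposed subjects and no clinically significant aminotransferase changes. That text does not say that nobody reached 3X ULN, and Phase 2 dosing lasted up to 12 weeks against 104 here, so no rate should be built on it.

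No endpoint, estimate or sample size changes. The conclusion rests on a literal reading of Section 8.7 and on the binder guidance not already ordering TBL at the Box C repeat. The change is worth making because it is cheap and concerns subject safety.

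**What to change.** In Section 8.7:

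- (a) Add TBL and ALP to the Box C step 1 repeat and to every later Box C repeat, and apply the trigger of TBL at least 2X ULN to the follow-up repeats in step 4.
- (b) Use one ALP condition in the selection factors, Box A, Box C step 3 and summary bullet 1. Whether ALP is kept or dropped is the sponsor's choice. If waiting for a confirmatory repeat when ALP is at least 2X is intended, say so.
- (c) Match summary bullet 1 to Box A step 3, so that both require an established cause and resolved abnormalities before drug can resume.

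If the ALP choice changes, check that Section 8.6 still fits, and check all of it against the ECI guidance in the site binder.

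The cost is a wording change plus two analytes that are already in Table 5, run on blood draws already planned.
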